#### 9.4.2 MISSING OUTCOMES DATA

We anticipate that there will be a very low amount of missing data for the outcomes of A1C and weight for study completers, since both measures are collected by the technician at the study visits. However, since the outcome of PA measurement relies on participants to wear the ActiGraph devices at 1-month intervals, there may be more missing data for this outcome variable. If more than 5% of data for this outcome variable is missing, the primary analysis will be based on multiple imputation. A sensitivity analysis will also be done using a complete case analysis (i.e. participants with 100% of PA data) and if results differ significantly, the primary analysis will be interpreted in light of results from the sensitivity analysis.

#### 9.4.3 BASELINE DESCRIPTIVE STATISTICS

Comparison of baseline characteristics between the intervention group and control groups will be conducted to assess the degree to which randomization was adequately achieved. Demographics (age, race, and gender), socioeconomic status (employment, education), comorbid conditions associated with metabolic syndrome (hypertriglyceridemia, hypertension, etc.) and factors relevant to the primary and secondary outcomes (baseline A1C, weight) will be reported. For normally distributed data, means and SDs will be shown. For non-normally distributed data, median and Interquartile range will be shown.

#### 9.4.4 COMPARISONS BY STUDY SITE

This trial will enroll participants from Johns Hopkins Hospital (JHH) and Reading Hospital. These two sites differ substantially with respect to the sociodemographics of the patient populations they serve. In addition, access to in-person DPPs (i.e. number of available programs) differs by site. For all of the outcome measures, sensitivity analyses will be conducted to account for study site to evaluate whether there may be differences in the treatment or response to treatment by the study site (JHH vs. Reading).

#### 9.4.5 COVARIATE ADJUSTMENT

We anticipate that randomization will minimize differences in participant characteristics that may be associated with the primary or secondary endpoints between the two groups. All primary statistical analyses will be unadjusted. However, if we identify differences in participant baseline characteristics, or exposure to potential confounders during the course of the study (e.g. steroid use, antihyperglycemic use), sensitivity analyses will be conducted to include these variables as covariates in multivariable logistic or linear regression models, as appropriate. These adjusted analyses will be viewed as supportive in interpreting the findings of the unadjusted analyses.

#### 9.4.6 WITHIN-GROUP ANALYSES

Several exploratory analyses will be undertaken within the hDPP and DPP arms only to evaluate factors associated with success in either group. In addition, though not a primary focus of this trial, we will conduct a single arm analysis of the hDPP arm only to explore differences in outcomes by study site (JHH vs. Reading), hDPP program site and/or hDPP program type (hospital based, primary care clinic, church, community).

#### 9.4.7 ANALYSIS OF THE PRIMARY EFFICACY ENDPOINT(S)

The primary effectiveness endpoint will be analyzed using an intention to treat approach (ITT) using logistic regression models, where attainment of the CDC's benchmark for type 2 diabetes risk reduction will be the dependent variable and treatment group the

primary exposure variable. Covariate-adjusted models will include any variables that are identified to be statistically significantly different on univariate analysis between the two treatment groups at baseline or over the study period, including use of medications that could influence blood glucose (antihyperglycemics, steroids) and incident diabetes.

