## 6.4 MEASURES TO MINIMIZE BIAS: RANDOMIZATION AND BLINDING

Block stratified randomization by baseline A1C level (5.7% to 6.0% vs. 6.1% to 6.4%) and recruitment site (JHU vs. Reading) will be done to ensure that the groups are balanced with respect to this variable, since higher A1C level at baseline is the strongest risk factor for progression to incident diabetes and potential need for glucose-lowering medications.

For several pragmatic reasons, this will be an open-label trial (i.e. treatment allocation will be unblinded to both participants and the study team). For efficiency, research coordinators conducting the home study visit will also be responsible for randomization and measurement of height and weight. Since the study team members will also need to interact with local DPPs, it would be practically challenging to blind the study team members to treatment assignment. The biostatistician will also be unmasked to treatment assignment and will provide required reports to the DSMB. The study team will have real-time access to all systems log data collected by Sweetch in the form of a dashboard.

Considering that hDPPs enroll participants to their programs on a rolling basis depending on the number of interested participants available to join a new cohort and availability of lifestyle coaches, it is possible that there will be times during the enrollment period where there may be an absence of available hDPPs to accept participants randomized to that arm in a timely fashion.

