## 9.3 POPULATIONS FOR ANALYSES

Consistent with the **intention-to-treat (ITT)** principle, results of all study participants will be evaluated according to initial randomization regardless of whether they adhered to their assigned treatment and regardless of protocol violations or deviations. Analyses of effectiveness endpoints, however, will exclude participants who withdraw from the study or withdraw consent. Effectiveness analyses will be performed for the ITT population. All primary statistical analyses of effectiveness measures will be unadjusted and two-sided tests of significance will be used. A per-protocol analysis will also be conducted using the population of program completers in each group, as defined in Section 3.3, to benchmark outcomes against CDC standards.

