## 9.4 STATISTICAL ANALYSES

### 9.4.1 GENERAL APPROACH

This clinical trial will be conducted under a common protocol with analyses conducted on pooled data from both sites. Data analyses will be conducted by a biostatistician. Exploratory data analysis will be performed to examine outliers, characterize the distributions of continuous and categorical measures, and track missing data. Mean, median, and frequency counts will be used to summarize baseline characteristics measured on a continuum, and proportions and frequency counts will be used for categorical measures. Baseline statistical differences in continuous measures between groups will be assessed using unpaired t-tests or Wilcoxon signed rank test, and statistical differences in categorical measures will be assessed using chi-square test or Fisher's Exact test as appropriate.

Between-group differences in primary and secondary outcomes will be evaluated in intention-to-treat analyses using mixed effects logistic regression models to account for potential within-program site clustering. For continuous measures in our secondary analyses, linear regression will be used to analyze the outcomes and for binary measures, logistic regression analyses will be used. Interaction terms will be used in regression models to evaluate effect modification.

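### The supportive adjusted models for the primary endpoint select covariates by significance testing and admit post-randomisation variables, including incident diabetes

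*Combined protocol and SAP*

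**What the plan says.** **Adjusted models.** Section 9.4.7 puts into the covariate-adjusted models whatever proves "statistically significantly different on univariate analysis between the two treatment groups at baseline or over the study period", and the named examples are "use of medications that could influence blood glucose (antihyperglycemics, steroids) and incident diabetes". Section 9.4.5 has a similar rule without the significance criterion: differences in baseline characteristics, or "exposure to potential confounders during the course of the study (e.g. steroid use, antihyperglycemic use"), prompt multivariable sensitivity analyses. On their standing, Section 9.4.5 says: "These adjusted analyses will be viewed as supportive in interpreting the findings of the unadjusted analyses".

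**Primary model.** Section 9.3 states: "All primary statistical analyses of effectiveness measures will be unadjusted". Section 9.4.5 repeats this. Section 9.4.1, however, describes the between-group comparison of primary and secondary outcomes as using "mixed effects logistic regression models to account for potential within-program site clustering". Section 9.4.7 mentions only logistic regression.

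**Stratification.** Section 6.4 specifies "Block stratified randomization by baseline A1C level (5.7% to 6.0% vs. 6.1% to 6.4%) and recruitment site (JHU vs. Reading"). Recruitment site returns in Section 9.4.4, where "sensitivity analyses will be conducted to account for study site". Baseline A1C is in no pre-specified between-arm model.

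**Related definitions.** Section 3.3 lists incident type 2 diabetes (A1C of 6.5% or more) as a secondary endpoint, with no time point. Section 3.2 lets a fall in A1C of at least 0.2 by 12 months satisfy the primary endpoint when baseline A1C is 5.7% to 6.4%.

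**The concern.** Randomisation removes confounding at baseline. A variable that arises afterwards may be a consequence of the assigned arm, so adjusting for it can remove part of the effect that the trial is meant to estimate. Section 9.4.5 labels in-study drug exposure as potential confounding, which it cannot be in this comparison.

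Incident diabetes is the clearest case, because it comes from the same measurement as one route to the primary endpoint. Antihyperglycemic use is tied to it: under Section 6.6 a study A1C of 6.5% or more prompts a letter to the physician, and drug treatment is then at the treating clinician's discretion. For steroids no section suggests a link with arm, so the objection there is timing alone.

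Selection by significance adds a second problem. The model is unknown until data by arm have been examined, and under Section 6.4 the biostatistician is unmasked. What is at stake is a supportive analysis that could make a real digital deficit look smaller than it is.

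**Working it through.** **Plan's own figure.** With 50% success in both arms, a 15-point margin, one-sided 5% and 80% power: n = (1.645 + 0.842)² × 2 × 0.25 / 0.15² = 137.4, so 138 per arm; 138 / 0.75 = 184. Both match Section 9.2. Nothing below changes them.

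**Overlap with the endpoint.** Section 8.2.2 excludes A1C of 6.5% or more at screening, so baseline is at most 6.4%. The A1C route then needs at most 6.4 − 0.2 = 6.2% at 12 months. A 12-month value of 6.5% or more therefore closes that route. A 6-month value does not, and the two weight routes stay open throughout.

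**Direction and size of the shift.** Let m be the proportion with incident diabetes in each arm, y₁ the success rate among those who develop it (same in both arms), and ȳ₀ the mean of the two arms' success rates among those who do not. Standardising over the pooled distribution of incident diabetes gives, to a close approximation,

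unadjusted − adjusted risk difference = (m_dDPP − m_hDPP) × (y₁ − ȳ₀).

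The sign is that of a product, so direction depends on both factors.

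Assumed inputs (none is in the documents): success without incident diabetes 52% in hDPP and 45% in dDPP, so ȳ₀ = 48.5%; success with it 20%. For 3% vs 6%: 0.03 × (20 − 48.5) = −0.86 points. The population-level logistic fit, which has no interaction term, gives −0.83. Results of that fit:

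| Incidence hDPP vs dDPP | Risk difference, unadjusted → adjusted (points) | Odds ratio |
|---|---|---|
| 2.6 vs 3.9% | −7.14 → −6.78 | 0.751 → 0.760 |
| 2 vs 4% | −7.36 → −6.81 | 0.744 → 0.759 |
| 3 vs 6% | −7.54 → −6.71 | 0.739 → 0.761 |
| 5 vs 10% | −7.90 → −6.51 | 0.727 → 0.765 |
| 5 vs 12% | −8.40 → −6.47 | 0.713 → 0.766 |

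With 30% success among those with incident diabetes, the shifts are 0.23, 0.35, 0.53, 0.88 and 1.21 points.

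**Cases where one condition fails.**
- Equal incidence, 5% in both arms: −6.65 before and after (odds ratio 0.765 → 0.762).
- Higher incidence in hDPP, 6 vs 3%: −5.83 → −6.71, away from no difference.
- 5 vs 12%, but 60% success among those with incident diabetes: −5.60 → −6.49, again away.

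**How often incident diabetes would enter.** Exact enumeration, 138 per arm, two-sided 5%, by chi-square (Fisher's exact in brackets; Section 9.4.7 names no test):
- 2.6 vs 3.9%: 8.2% (4.0%)
- 3 vs 6%: 21.6% (13.6%)
- 5 vs 10%: 35.4% (26.8%)
- 5 vs 12%: 56.5% (47.2%)
- 5% in both arms: 4.8% (2.3%)

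The shifts in the table are not conditional on entry. Selection widens the imbalance: at 3 vs 6%, trials in which the variable enters by chi-square average about 1.7 vs 8.0%. The formula then gives roughly 0.063 × 28.5 = 1.8 points.

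**Chance selection at baseline.** With k independent baseline variables tested at 5%, the chance that at least one is significant is 1 − 0.95^k: 23% for k = 5 and 40% for k = 10. The documents do not close the list, so k is an assumption.

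**Stratification factors.** Two equal strata, mean success 50%, 138 per arm. The unadjusted standard error is √(0.5/138) = 0.0602; the stratified one is √(2(0.25 − d²)/138), with d half the gap between strata.

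| Gap between strata | Stratified SE | Power, unadjusted / stratified | Type I error, unadjusted |
|---|---|---|---|
| 10 points | 0.0599 | 80.3 / 80.5% | 4.9% |
| 20 points | 0.0590 | 80.6 / 81.6% | 4.7% |
| 40 points | 0.0552 | 82.2 / 85.9% | 3.6% |

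No section supports a gap of 40 points. A separate simulation with four strata (20,000 runs) found power of 82% unadjusted and 81-82% stratified in three of four scenarios, and 84 vs 86% in the fourth, which had the most strongly prognostic strata.

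**The case against.** Much can be said for the plan. The primary analysis is pre-specified as unadjusted, the adjusted models are expressly supportive, and no section tests them against the margin. Section 9.4.9 expects few participants to convert to diabetes, and at low incidence the illustrated shift is under 1 point against a margin of 15. All of this stands, and it limits the weight of the point.

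A reader might infer that adjusting for incident diabetes always flatters the digital arm when that arm is worse. The documents do not support this. It needs higher incidence in dDPP and lower success among those affected, and neither is assured. Section 3.3 sets no time point, so a 6-month value counts. Section 7.2 keeps such participants in the trial, and with or without treatment their 12-month A1C or weight may still qualify.

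The medication adjustment also has a legitimate purpose. If more digital-arm participants started antihyperglycemics and this raised their success, the unadjusted comparison would favour the digital arm, and the planned adjustment is the only between-arm check on that. Deleting it with nothing in its place would leave a gap. This stands too, and the fix must name a replacement.

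Finally, leaving out the stratification factors might be read as invalidating the primary test. It does not: the test stays valid and slightly conservative.

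**Conclusion.** The defect is in the wording of Sections 9.4.5 and 9.4.7 and is plain from the text. Followed as written, the rule can produce a supportive estimate that conditions on a consequence of treatment and partly on the outcome itself. The primary estimate is not biased by it.

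When both conditions hold, the shift toward no difference is about 0.4 to 0.8 points at low incidence (2.6 vs 3.9% to 3 vs 6%) and 1.4 to 1.9 points at 5 vs 10-12%. These figures rest on assumed success rates of 52%, 45% and 20%, and do not condition on the variable having entered the model. They illustrate the mechanism and do not predict the result. No rate of changed conclusions can be derived, because the plan attaches no decision rule to the adjusted models.

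The stratification point is minor: a small gain in precision at most. Sections 9.4.1 and 9.4.7 do need to be reconciled, since together they leave the form of the primary model unclear. The changes should be made, but the validity of the primary test does not depend on those to the adjusted models.

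**What to change.** 1. **Sections 9.4.5 and 9.4.7:** remove incident diabetes and in-study medication use as covariates, and report both by arm. Address drug starts in a named sensitivity analysis with a stated intercurrent-event strategy, beside the unchanged unadjusted treatment-policy primary analysis. One example is a composite strategy that counts participants who start antihyperglycemics as not meeting the endpoint.
2. **Selection:** replace significance-based selection with a fixed list of baseline covariates, stated once, so that the two sections no longer give different entry rules.
3. **Named supportive adjusted analysis:** include recruitment site and baseline A1C. Use A1C as a continuous value, because Section 5.1 also admits participants on glucose criteria while the strata in Section 6.4 cover only 5.7% to 6.4%. Report a standardised risk difference with its confidence limit, read against the 15-point margin.
4. **Section 9.4.7:** state how the program-site mixed model of Section 9.4.1 applies to the primary analysis.

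The cost is analysis-plan wording. The variables are already collected, the sample size does not change, and items 1 to 3 leave the primary estimator as it is. Because the biostatistician is unmasked, all four items should be settled before outcome data are examined by arm.

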#### 9.4.8 ANALYSIS OF THE SECONDARY ENDPOINT(S)

Secondary endpoints will also be analyzed according to the ITT principle. Each of the individual outcomes in the CDC's benchmark for type 2 diabetes risk reduction (a composite endpoint) will be analyzed as a secondary endpoint at both the 6- and 12-month time points. As with the primary effectiveness endpoint, each outcome will be analyzed using logistic regression models. In addition, we will analyze change in A1C, absolute weight change and percentage weight change as continuous measures using linear regression models. Various physical activity measures will be analyzed as continuous measures, including average minutes/week of PA (light, moderate, intense), MET-hours per week of PA, and average number of steps per day. For responses from acceptability questionnaire (Likert-scale questions), non-parametric tests such as Spearman's correlation or chi-square test for independence will be used. For overall Likert scale scores, parametric tests such as Pearson's correlation or t-test will be used.

We anticipate that there will be a very low amount of missing data for the outcomes of A1C and weight for study completers, since both measures are collected by the research coordinator at the study visits. However, since the outcome of PA measurement relies on participants to wear the ActiGraph devices at 1-month intervals, there may be more missing data for this outcome variable. If more than 5% of data for this outcome variable is missing, the primary analysis will be based on multiple imputation. A sensitivity analysis will also be done using a complete case analysis (i.e. participants with 100% of valid PA data) and if results differ significantly, the primary analysis will be interpreted in light of results from the sensitivity analysis.

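### Section 9.4.8 does not prespecify the outcome's own baseline value in the main models for the continuous secondary outcomes, which gives up precision, mainly for A1C

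*Combined protocol and SAP*

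**What the plan says.** Section 9.4.8 sets the method for three continuous outcomes: "we will analyze change in A1C, absolute weight change and percentage weight change as continuous measures using linear regression models". It lists no covariates. For the activity measures it says only that they are treated as continuous. It gives no method for the WHO-5 score, which appears as an endpoint in Section 3.3. The general rule in Section 9.4.1 is "For continuous measures in our secondary analyses, linear regression will be used to analyze the outcomes", again with no baseline term.

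Two sections deal with adjustment. Section 9.3 states "All primary statistical analyses of effectiveness measures will be unadjusted". Section 9.4.5 repeats "All primary statistical analyses will be unadjusted" and then says what happens if baseline differences or in-study exposures are identified: "sensitivity analyses will be conducted to include these variables as covariates in multivariable logistic or linear regression models, as appropriate". Their status is set by "These adjusted analyses will be viewed as supportive in interpreting the findings of the unadjusted analyses".

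The baseline values exist. Section 9.4.3 says that "factors relevant to the primary and secondary outcomes (baseline A1C, weight) will be reported", and the schedule in Section 1.3 has A1C and weight measured at the baseline visit. Randomisation uses baseline A1C as well: "Block stratified randomization by baseline A1C level (5.7% to 6.0% vs. 6.1% to 6.4%) and recruitment site (JHU vs. Reading"). No section places the outcome's own baseline value, or the A1C stratum, in a main model. ANCOVA appears only in the abbreviation list in Section 10.2.

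**The concern.** In a randomised trial, a model that includes the baseline value of the outcome is never less precise than the simple change score, apart from a lost degree of freedom. The gain is there whether or not the arms look balanced, so a rule that adds covariates only after a difference is seen does not secure it. The triggered model may also not contain the right variable: Section 9.4.5 allows exposures arising during the study, such as steroid or antihyperglycemic use, and does not require the baseline value.

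What is at stake is the width of the intervals for A1C and weight change. These outcomes help a reader interpret the composite primary endpoint, and Section 9.4.9 uses change in A1C as the proxy for future diabetes incidence in the lifetime economic model. Section 6.4 makes the trial open-label with an unmasked biostatistician, so a choice between the two models made after seeing data would be open to challenge. A choice written into the plan would not.

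**Working it through.** **The plan's own figure.** Section 9.2 assumes 50% success in both arms, a 15-point margin, a one-sided 95% limit and 80% power. Then n = (1.645 + 0.842)² × 2 × 0.5 × 0.5 / 0.15² = 137.4, so 138 per arm, and 138 / 0.75 = 184 after 25% attrition. Both figures reproduce. They concern the binary primary endpoint; no sample size is stated for the continuous outcomes.

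**Inputs.** n = 138 analysable per arm (Section 9.2) and two-sided 5% tests (Section 9.3). The baseline SD s0, follow-up SD s1 and baseline to follow-up correlation rho are not in the documents and are assumed over a range.

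**Formulas, variance per participant.**

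- Change score: s0² + s1² − 2·rho·s0·s1
- Baseline-adjusted: s1²(1 − rho²)
- Saving (the difference): (s0 − rho·s1)², which is never negative
- With s0 = s1, the ratio adjusted/change is (1 − rho²) / [2(1 − rho)] = (1 + rho)/2

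**Equal SDs.** The matching n is 138 / ratio. Power is for an effect that the change score detects with 80% power.

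| rho | variance ratio | variance reduction | interval width factor | change-score n per arm matching 138 adjusted | power after adjustment |
|---|---|---|---|---|---|
| 0.3 | 0.65 | 35% | 0.81 | 212.3 | 93.5% |
| 0.5 | 0.75 | 25% | 0.87 | 184.0 | 89.9% |
| 0.7 | 0.85 | 15% | 0.92 | 162.4 | 86.0% |
| 0.95 | 0.975 | 2.5% | 0.99 | 141.5 | 81.0% |

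A simulation of 3,000 trials per setting, 138 per arm, gave ratios of 0.654, 0.759, 0.845 and 0.980.

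**Unequal SDs.** With k = s1/s0, the ratio is k²(1 − rho²) / (1 + k² − 2·rho·k).

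- rho 0.5, k 1.25: 1.1719 / 1.3125 = 0.893, a reduction of 10.7%
- rho 0.5, k 1.5: 1.6875 / 1.75 = 0.964, a reduction of 3.6%
- rho 0.3, k 1.25: 1.4219 / 1.8125 = 0.784, a reduction of 21.6%
- rho 0.3, k 1.5: 2.0475 / 2.35 = 0.871, a reduction of 12.9%

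The saving vanishes where rho·k = 1, for example at rho 0.9 with k about 1.1.

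**Percentage weight change.** This outcome is already scaled to baseline. In a simulation where it was unrelated to baseline weight, the ratio was 1.00: no gain and no loss.

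**The case against.** The strongest objection is textual. A reader might infer that the plan states a model with arm alone. It does not: Section 9.4.8 is silent on covariates, and the unadjusted rule in Sections 9.3 and 9.4.5 refers to primary statistical analyses, which could mean only those of the primary endpoint. The broader reading is better supported, because Section 9.4.5 speaks of primary or secondary endpoints and of linear as well as logistic models, and no other text supplies a baseline term. What is certain is that the baseline value is not prespecified.

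A reader might also infer that every continuous outcome loses a quarter or more of its precision. The documents do not support that. The (1 + rho)/2 rule needs equal SDs, and two of the three outcomes named in Section 9.4.8 may gain little or nothing.

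Nor can one conclude that A1C must sit at the large-gain end because entry restricts its range and a point-of-care device reads it. Restriction at entry but not at follow-up could make the follow-up SD larger, which shrinks the gain at low to moderate correlations. The restriction is also partial: Section 5.1 admits participants on glucose results, and Section 3.2 limits only the A1C component of the composite to a baseline of 5.7% to 6.4%.

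Chance imbalance is partly handled by stratifying on A1C and by the triggered sensitivity analyses. That stands, but neither step recovers the precision. Finally, a blanket instruction to adjust every outcome for baseline would go too far. Section 6.1 mails the digital kit so that baseline activity can be recorded before the intervention starts, which places the Actigraphy baseline week after allocation in an open-label trial. That baseline could itself be affected by knowing the arm.

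**Conclusion.** The point holds as a matter of efficiency. The main models for the continuous secondary outcomes have no prespecified baseline term, and the sections read together make those comparisons unadjusted. Nothing here biases the comparison, and neither the primary endpoint nor the 138 and 184 per arm is touched.

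The size depends on SDs and correlations that the documents do not give. It is material for A1C if the correlation is moderate and the SDs are similar: at 0.5, the unadjusted analysis would need 184 per arm to match 138 adjusted. It could be only a few percent if follow-up A1C is much more variable than baseline. It is small for absolute weight at a correlation near 0.95 with similar SDs, and about zero for percentage weight change. The change is worth making because it is nearly free, but it is of modest priority.

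**What to change.** In Section 9.4.8, state that change in A1C and change in weight are analysed by linear regression on arm, the outcome's own baseline value and the stratification factors (baseline A1C level and site), as the main model and regardless of observed imbalance. Keep the unadjusted change as the supportive analysis. Amend Sections 9.3 and 9.4.5 so that the unadjusted rule does not contradict this. For absolute change, the estimated arm effect is the same as from regressing the follow-up value on the same terms, so the endpoint definition need not change.

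Apply the same model to WHO-5 if it is analysed as a continuous change, and name that method. For Actigraphy, report baseline-adjusted and unadjusted results, with the caveat that the baseline week is worn after allocation. The strata in Section 6.4 start at 5.7%, so say how any randomised participant with a lower baseline A1C is coded. A repeated-measures model of the 6- and 12-month values is optional.

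The cost is SAP wording and a degree of freedom per added term. No new data are needed.
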